like to receive an electronic copy of their personalized drinking feedback report and/or a list of local services for mental health- and substance-related concerns. Providing an email address will be completely voluntary. All email addresses collected will be deleted after the data have been downloaded to the CAMH secure server. To ensure participants are aware that their email address will be connected to their data, we have included the following text in the consent form: “It is recommended that for the report, you use an email address that does not identify you (for example, that you use an email that does not include your first or last name or other information that could identify you). This is because the email address you provide for the report will be temporarily stored in a secure Qualtrics database and will be connected with your data. If you use identifiable information in your email, the Qualtrics database may be able to link you to the data you provide (i.e., your data will be identifiable in the Qualtrics database). The choice is yours, and the research team would like to make you aware of this.” TAU participants will receive no intervention.

Follow Up Sessions

At 3-month and 6-month follow-up visits, all participants will complete similar questionnaires to the baseline survey/screener measuring the same constructs in order to identify any changes in outcomes over time. DBS samples from finger prick will also be obtained at these follow up visits to test PrEP adherence and alcohol use biomarkers (see “Dried Blood Spot Testing” and “Measures” below, as well as the corresponding attachments). For participants in the intervention arm only, an additional questionnaire will be included at the end of the 6-month assessment to evaluate the perceived acceptability of the intervention (included in the “Survey” attachment). With participants’ explicit written consent, retrospective chart reviews will be conducted by CAMH research staff for aspects pertaining to PrEP treatment-related factors; alcohol, substance use, and mental health-related aspects; incident STIs; and other relevant clinical indicators (see “Chart Review” attachment). Chart review items were previously approved in the first phase of this study (CAMH REB# 101/2017-03; UHN REB# 18-5014.3).

Dried Blood Spot Testing

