Alcohol consumption. Behavioral measures and a biomarker test will be employed to evaluate **Specific Aim 2**. The AUDIT,²⁰ included as part of the pre-screening process at baseline, will be incorporated into 3-month and 6-month follow-up assessments to identify changes in hazardous drinking over time. Two supplemental self-report alcohol items will be included in all assessments to measure 1) the number of drinks consumed in a typical week, and 2) the highest number of drinks consumed on a single occasion.²⁹ As an objective measure of alcohol use, an alcohol derivative, phosphatidylethanol (PEth), will be assessed from dried blood spots (DBS) obtained at baseline, 3-months, and 6-months. PEth has been shown to be highly correlated with several measures of alcohol consumption;³⁰ it has been used as a clinical marker for chronic excessive drinking and binge drinking;³⁰⁻³⁴ and has been employed as a primary outcome in alcohol treatment trials.^{35,36} The half-life of PEth has an estimated range of 4-12 days, and it has demonstrated a high degree of sensitivity (i.e., >95%) and specificity (i.e., 100%) when comparing patients presenting for alcohol treatment to those who abstain or only consume alcohol at low levels.³⁷⁻⁴¹ PEth levels will be measured using liquid chromatography-tandem mass spectrometry, and values will be examined based on a dichotomy using a cut-off of ≥ 35 ng/ml to identify hazardous drinking.⁴²

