Statistical analyses. Analyses pertaining to feasibility and acceptability indicators (**Aim 1**) will be based on descriptive statistics involving frequency counts (e.g., intervention completion rates) and mean scores (i.e., acceptability measure). The anticipated patterns pertaining to **Aims 2, 3, and 4** will be tested with generalized linear mixed effect models including random intercepts for every patient,^{61,62} based on the expectation that the intervention group will have better outcomes at both follow-up time points. Mixed effect models have fewer assumptions compared to more

traditional repeated measures of analyses of variance⁶¹ with respect to missing values.^{63,64}

For the quantification of the causal impact of alcohol, we will additionally use path models, where alcohol consumption levels will be introduced into the equations, with the hypothesis that the introduction of this variable will make the differences between experimental and control groups disappear.

Reference List

1. Public Health Agency of Canada. (2015) HIV and AIDS in Canada: Surveillance Report to December 31, 2014. Ottawa: Minister of Public Works and Government Services Canada. Available at: <http://www.phac-aspc.gc.ca/aids-sida/publication/epi/2010/index-eng.php>. Accessed April 13 2017.
2. Public Health Agency of Canada. (2015) Summary: Estimates of HIV Incidence, Prevalence and Proportion Undiagnosed in Canada, 2014. Available at: <http://healthycanadians.gc.ca/publications/diseases-conditions-maladies-affections/hiv-aids-estimates-2014-vih-sida-estimations/index-eng.php>. Accessed April 13 2017.

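### PEth, the only objective Aim 2 alcohol measure, is planned only as a cut at 35 ng/ml; a log-concentration analysis should be added as its main analysis

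*Combined protocol and SAP*

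**What the plan says.** Under Outcome Measures, Alcohol consumption, the blood marker "phosphatidylethanol (PEth), will be assessed from dried blood spots (DBS) obtained at baseline, 3-months, and 6-months". The assay gives a concentration: "PEth levels will be measured using liquid chromatography-tandem mass spectrometry". The same sentence then says that "values will be examined based on a dichotomy using a cut-off of" ≥ 35 ng/ml, with the stated purpose of identifying hazardous drinking and a cited source for the threshold.

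The other Aim 2 measures in that section are the AUDIT and two drink-count items, all self-reported. The chart review also collects alcohol-related items, but they are not listed as Aim 2 outcomes.

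Under Data Analysis, Statistical analyses, Aims 2 to 4 are to be tested with "generalized linear mixed effect models including random intercepts for every patient", on the expectation that "the intervention group will have better outcomes at both follow-up time points". No scale is given there for PEth. No log-scale, continuous or change analysis of PEth is stated anywhere.

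**The concern.** Aim 2 asks whether the intervention reduces alcohol consumption, which is a question of amount. The cut answers a narrower question: on which side of 35 ng/ml a man falls. A man whose PEth drops sharply but stays above the cut is scored as unchanged. A man already below it at baseline cannot register an improvement. Entry is by AUDIT-C score, not PEth, so men may start on either side.

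PEth carries particular weight because of the comparison group. The Intervention section says that "TAU participants will receive no intervention", so men can tell whether they had the drinking feedback, and their self-reports may be affected by that. PEth is the check on those reports. A less precise PEth result makes a real reduction easier to miss and gives a weaker estimate of preliminary impact for planning a later trial.

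**Working it through.** **The plan's own figure.** There is none to reproduce. The Statistical power paragraph concerns PrEP adherence and gives no figure for PEth.

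**Inputs from the documents.** 120 men at 2:1, so 80 intervention and 40 TAU; PEth at baseline and two follow-ups; cut at 35 ng/ml.

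**Inputs assumed, because the documents do not give them.** Normal log PEth with equal correlation ρ between visits, 0.3 to 0.7; share p of TAU men above the cut, 50%, 70% or 85%; effect size; share undetectable; two-sided 5% test. Complete follow-up and a uniform shift are assumed unless stated.

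**Step 1: information kept by the cut (small effect, mean of two follow-ups, no baseline, no censoring).**

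E = [φ(z_p)² / (p(1−p))] × (1+ρ)/(1+ρ_b), where ρ_b is the correlation between the two binary values, taken from the bivariate normal.

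- Best case, p = 0.5, ρ = 0.7: 0.3989²/0.25 = 0.637; ρ_b = 0.494; E = 0.637 × 1.7/1.494 = 0.725. Loss 27.5%; 120 men count as 120 × 0.725 = 87.
- Worst case, p = 0.85, ρ = 0.3: 0.2332²/0.1275 = 0.426; ρ_b = 0.149; E = 0.426 × 1.3/1.149 = 0.482. Loss 51.8%; 120 men count as 58.

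| p above cut | E at ρ = 0.3 / 0.5 / 0.7 | Loss |
|---|---|---|
| 50% | 0.693 / 0.716 / 0.725 | 28-31% |
| 70% | 0.633 / 0.655 / 0.662 | 34-37% |
| 85% | 0.482 / 0.501 / 0.504 | 50-52% |

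The range moves with the setting. If p goes no higher than 80%, the upper end is 45%. At an effect that the continuous analysis detects with about 80% power, the simulated loss is 25-38%, or 20-33% if 10% of TAU values sit at an assay floor. If baseline is used as a covariate in the same form as the outcome, the small-effect loss is about 36-71%.

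**Step 2: power for the contrast recommended below.** Simulated, 80 v 40, mean of both follow-ups adjusted for baseline by least squares, no censoring, 6,000 trials per cell. A 0.5 SD shift moves the share above the cut from 50% to 31%, 70% to 51%, or 85% to 70%.

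| 0.5 SD shift | Cut, ρ = 0.3 / 0.5 / 0.7 | Log PEth, same ρ |
|---|---|---|
| p = 50% | 77.8 / 77.7 / 80.0 | 93.0 / 95.3 / 98.8 |
| p = 70% | 75.9 / 75.6 / 79.8 | 92.0 / 94.8 / 98.8 |
| p = 85% | 65.5 / 65.0 / 67.7 | 92.7 / 95.2 / 98.7 |

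At 0.3 SD the figures are about 27-40% against 52-73%. With no effect, both analyses reject in about 5% of trials.

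**Step 3: does the result depend on least squares?** A random-intercept logistic model of the cut was compared with a left-censored random-intercept model of log PEth. Both took baseline as a response with equal arm means and tested one arm effect common to both follow-ups. At 0.5 SD with 10% undetectable, power is 69-80% against 93-99%.

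**Step 4: less favourable settings at 0.5 SD.**

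- 40% undetectable, p = 50%, models of Step 3: 77.7 / 79.6 / 80.1 against 87.3 / 90.3 / 96.3, a gain of 9.6, 10.7 and 16.2 points. If undetectable values are instead set to the assay floor in the least-squares analysis (60,000 trials), the gain is about 7, 9 and 12 points.
- Half the intervention men shift 1.0 SD and half do not shift (Step 3 models, 10% undetectable): 68-79% against 88-97%.
- 20% fewer men, 64 v 32 (Step 3 models, 10% undetectable): 58-70% against 89-97%.

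The continuous analysis does better in every setting.

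**The case against.** The strongest case for leaving the plan alone is that this is a pilot. The Statistical power paragraph calls it a feasibility study, Aim 2 seeks preliminary impact, PEth is one of four Aim 2 measures with none named primary, and the concentrations will exist and could be analysed later. The threshold has a stated purpose and a source, and it matches the hazardous-drinking population. All of this stands. It limits the stakes and is why the cut should be kept. It does not remove the gain from stating the more precise analysis in advance, since one chosen after the results are seen is weaker evidence.

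A second objection is that the simulations favour the continuous model, because the data follow the form that it fits. That is partly right. A non-uniform effect and heavy censoring were tried; a separate spike of undetectable values and non-normal tails were not.

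Some stronger readings are tempting but not supported:

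- A reader might infer that 28-52% is this trial's loss. It is a conditional figure, and none of its inputs is in the documents.
- A reader might infer that the cut is an error or destroys the objective check. Dichotomised PEth is still objective; the cost is precision.
- A reader might infer that baseline PEth is meant to be a repeated response, because Follow Up Sessions speaks of "measuring the same constructs in order to identify any changes in outcomes over time". That sentence is about questionnaires; blood spots come in the next one.
- A reader might count the path models as the missing analysis, since "alcohol consumption levels will be introduced into the equations". That text does not name PEth and concerns mediation, not the arm effect on PEth. What it means is a separate question and no evidence for this point.

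**Conclusion.** The point holds as a low-cost improvement. The only stated analysis of the one objective Aim 2 measure discards information on how far drinking fell. The direction was the same in every setting examined; the size is not known for this trial.

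Under the assumptions listed, the small-effect, no-baseline loss is about 28-52%, and it is smaller at larger effects or with many undetectable values. For an assumed 0.5 SD shift averaged over both follow-ups with baseline adjustment, power is about 65-80% with the cut and 92-99% with log PEth. With 40% undetectable the gain is roughly 7-16 points, depending on how those values are handled. The loss figure and the power figures describe different analyses (without and with baseline) and should not be read as one result.

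**What to change.** In Outcome Measures (Alcohol consumption) and Statistical analyses, state that:

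- The main PEth analysis is a linear mixed model of log PEth at 3 and 6 months with a random intercept, arm, time and arm-by-time, adjusted for baseline log PEth.
- Undetectable values are treated as left-censored. If baseline values are also undetectable, baseline may instead enter as a response with arm means constrained equal.
- The main contrast is the arm effect averaged over the two follow-ups, reported as a geometric mean ratio with 95% CI. The 3-month and 6-month estimates are supporting results.
- The proportion at or above 35 ng/ml is kept as a supporting result, because it matches the trial's hazardous-drinking construct.

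This changes wording only: no extra samples, visits or assays. The downsides are that a ratio is less intuitive than a proportion, which is why the proportion is still shown, and that the gain shrinks if many values are undetectable.

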Study Protocol

Name of Study: PrEP and Alcohol

Responsible Investigators:

Principal Investigator: [name], Centre for Addiction and Mental Health (CAMH).

Co-Investigators: [name], Toronto General Hospital.
[name], CAMH.
[name], Maple Leaf Medical Clinic.
[name], CAMH.

NOTE: This research is based on an NIH/NIAAA UH2/UH3 grant mechanism that involves a two-phased approach (i.e., UH2 Phase: Years 1-2; UH3 Phase: Years 3-5). REB approval for UH2 phase (years 1-2) was initially obtained on October 2, 2017 (CAMH REB# 101/2017; UHN REB#18-5014). Recruitment for this phase is now completed. The present protocol covers studies for the second phase of the grant, UH3, which was funded in September 2019 and has an anticipated end date of August 2022.

I. Introduction and Background

HIV continues to pose a significant public health concern in Canada, with recent estimates indicating approximately 75,500 Canadians living with HIV.¹ Within the context of this epidemic, HIV disproportionately impacts gay, bisexual, and other men who have sex with men (MSM), who comprise approximately half of all new and existing HIV infections in Canada.²

HIV-negative (HIV-) MSM have traditionally been reliant on condoms as their primary method of preventing HIV acquisition through sexual contact. More recently, however, biomedical strategies have moved to the forefront of prevention, with HIV pre-exposure prophylaxis (PrEP) offering those who are HIV- an effective new method of protection from the virus. PrEP entails taking a daily dose of tenofovir disoproxil fumarate/emtricitabine, which prevents HIV from replicating and taking hold inside one's body. Empirical support for PrEP has been strong, with several randomized controlled trials (RCTs) providing evidence for its efficacy; showing a reduction in the rate of HIV infection by 44%-86%.³⁻⁷

Although PrEP is an effective tool in preventing the acquisition of HIV,³⁻⁷ its effectiveness has been shown to be dependent on a number of key behaviors, including adherence to the treatment,^{4,6-9} attendance in follow-up care, and the continued use of condoms.

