- 2) Assess the preliminary impact of an alcohol-focused brief intervention on reducing alcohol consumption among a sample of hazardous drinking, PrEP-prescribed MSM.
- 3) Assess the preliminary impact of an alcohol-focused brief intervention on improving PrEP adherence and retention in PrEP-related care among a sample of hazardous drinking, PrEP-prescribed MSM.
- 4) Assess the preliminary impact of an alcohol-focused brief intervention on reducing condomless sex and STIs among a sample of hazardous drinking, PrEP-prescribed MSM.

IV. Study Design

We will conduct a pilot randomized controlled trial (RCT) of an alcohol-focused brief intervention with supplementary modules that focus on concurrent substance use and depression.

A total of 120 PrEP-prescribed MSM who are hazardous drinkers will be recruited from two medical clinics, Toronto General Hospital (TGH) and Maple Leaf Medical Clinic (MLMC), located in downtown Toronto. Participants will be randomly assigned to either the intervention condition or treatment as usual (TAU) based on a 2:1 intervention:TAU ratio. All participants will complete biological and behavioral measures at baseline and at 3- and 6-months post-baseline to assess PrEP-related behaviors, alcohol consumption, substance use, and depression. An overview of the trial design is depicted in Figure 1.

Figure 1. Pilot RCT design overview.

Eligibility Criteria

To be included in the study, participants must be (a) aged 18 years or older, (b) be a patient of TGH or MLMC, (c) be a man who identifies as a gay or bisexual, and/or a man who has sex with other men, (d) have been prescribed PrEP for at least 3 months, and (e) meet the criteria for hazardous drinking, (i.e., based on a score of ≥ 4 on the Alcohol Use Disorders Identification Test – Consumption measures (AUDIT-C))²⁰

Participants will be excluded if they do not meet all of the above-mentioned inclusion criteria.

Study Procedures and Measures

Men presenting for routine PrEP-related care at TGH and MLMC will be made aware of the study either through TGH/MLMC clinic staff members (e.g., doctors, nurses, clinic research staff) or via study information cards and/or posters (see “Recruitment Ad” attachment) at their respective clinics. Interested individuals will be referred to a CAMH research staff member. The CAMH research staff member will provide additional information about the study (see “Pre-Screening Script” attachment) and answer any questions that the individual may have.

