PrEP adherence. Adherence to PrEP will be assessed at baseline, 3-months, and 6-months using a combination of behavioral and biological assessments to evaluate the adherence-focused component of **Specific Aim 3**. The behavioral assessment will be comprised of adapted versions of two well-validated measures of adherence,^{43,44} identifying 1) the number of missed PrEP doses over the past seven days; and 2) the percent of PrEP doses taken over the past four weeks. These measures have been employed in a number of intervention trials and provide good estimates of adherence.⁴⁵ For both measures, suboptimal adherence will be defined as taking <80% of one's prescribed PrEP doses.¹¹ DBS samples obtained at baseline, 3-, and 6-months will be analyzed for quantities of PrEP components (e.g., tenofovir/emtricitabine (TFV/FTC)), using a validated liquid chromatography tandem mass spectrometry method widely used in PrEP research.^{6,9,46-55} The half-life of TFV is 15 hours and that of FTC is 10 hours⁵⁰ which will allow the quantification of recent use of PrEP with a single DBS sample. Furthermore, blood plasma has been shown to provide a good indication of PrEP use for periods ranging from 24 hours to seven days.^{50,51,54} A cut off for the concentration of ≤ 10 ng/ml (for either TFV or FTC) will be employed, as this has been shown to be indicative of inconsistent PrEP intake.^{50,51}

Retention in care. **Specific Aim 3** includes an additional focus on retention in PrEP-related care. Attendance at clinic visits that correspond with 3- and 6-month assessments, and attendance during any other regularly scheduled PrEP clinic visits during the 6-month follow-up period, will be used as an indicator of retention.

Engagement in condomless sex. In accordance with **Specific Aim 4**, condomless sex will be assessed at baseline and follow-up study visits using an adapted version of a validated MSM-focused sexual behavior assessment that queries condom use during the past three months.⁵⁶ Responses at each time point will be dichotomized to identify participants who engaged in any condomless anal sex. As an objective indicator of condomless sex, incident chlamydia, gonorrhea, syphilis, and HCV, diagnosed at each time point, will be identified through chart extraction.

Additional Measures

Participant characteristics. Demographic factors to be collected include age, race, educational background, and income. These factors will be queried during the baseline assessment.

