Substance use and Depression. Substance use other than alcohol will be assessed using the National Institute on Drug Abuse (NIDA) - Modified Assist Screening Tool (NIDA M-ASSIST).⁵⁷ This measure queries lifetime use of a variety of substances, frequency of substance use during the past three months, and negative consequences experienced as a result of substance use. Participants will be identified as possessing a potential substance use issue based on NIDA M-ASSIST scoring. Participants will complete the Center for Epidemiologic Studies Depression Scale-10 (CESD-10).⁵⁸ A score ≥ 10 will be used as an indicator of the presence of marked depressive symptomatology.⁵⁸ Both measures will be administered at baseline and at the two follow-up time points.

It should be noted that the demographic and behavioral measures (i.e. alcohol consumption, PrEP adherence, retention in care and engagement in condomless sex) included in this study were previously approved in the first phase of this study (CAMH REB# 101/2017-02; UHN REB# 18-5014).

Data Analysis

Statistical power. As this is a feasibility study and not intended as a definitive clinical trial, sample size considerations focus on expected effect sizes detectable with the design. The following effect size for the variable that likely has the least power (i.e., adherence –**Aim 3**) can be detected based on the following assumptions: there is a combined effect of 1) the suggested alcohol intervention on alcohol intake,⁵⁹ and 2) the effect of lowered alcohol intake on PrEP adherence.¹¹ Suboptimal PrEP adherence, defined as taking $<80\%$ of all doses, was estimated based on the literature¹¹ and assumed to be 30% among heavy alcohol users.⁸ With the current sample size, we would be able to significantly detect Odds Ratios of 3 and higher, and assuming confounding with an R^2 of other variables on the dependent variable, Odds Ratios of 3.5 and higher. We will be able to detect differences in proportions of about 20% with a 95% Confidence Interval between 2% and 28%.⁶⁰ Other factors in **Aims 2, 3, and 4** can detect smaller effect sizes.

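### On seven daily doses the <80% rule is exactly missed 2 or more, a noisy indicator of overall adherence that gives up power usually available in the count itself

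*Combined protocol and SAP*

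**What the plan says.** The PrEP adherence paragraph under Outcome Measures (IV. Study Design) lists two self-report items: "the number of missed PrEP doses over the past seven days" and "the percent of PrEP doses taken over the past four weeks". One cut then serves both: "For both measures, suboptimal adherence will be defined as taking <80% of one's prescribed PrEP doses". A dried-blood-spot (DBS) drug level is collected as a third adherence measure.

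The Introduction describes daily dosing: "PrEP entails taking a daily dose of tenofovir disoproxil fumarate/emtricitabine".

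The Statistical power paragraph treats adherence as the outcome likely to have the least power. It defines suboptimal adherence as under 80% of all doses, with a rate "assumed to be 30% among heavy alcohol users". It adds that "we would be able to significantly detect Odds Ratios of 3 and higher" and "We will be able to detect differences in proportions of about 20% with a 95% Confidence Interval between 2% and 28" per cent. It does not say which adherence measure these figures refer to. It gives no direction for the difference, no power level and no distribution of adherence between men.

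The Statistical analyses paragraph tests Aim 3 with generalized linear mixed models that have a random intercept per patient, using both follow-up visits.

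**The concern.** One percentage cut is applied to two items of very different resolution. On seven doses no observable value lies between 71% and 86%, so a single further missed dose moves a man across the cut. A man whose usual adherence is comfortably above 80% will often have a bad week, and a man below 80% will often have a good one.

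Two things are at stake. First, when such errors occur in both arms they pull the Aim 3 difference on this item towards zero, while the count that would lose less is already recorded. Second, both binaries carry the same 80% label, so chance disagreement between them at one visit could be read as a finding about behaviour or about the measures.

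**Working it through.** **Inputs from the protocol.** 120 men ("A total of 120 PrEP-prescribed MSM who are hazardous drinkers will be recruited"), allocated 2:1, so 80 intervention and 40 TAU; daily dosing; the <80% cut; 30% suboptimal; a detectable difference of about 20 points.

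**Assumptions not in the protocol.** Two-sided 5% test; one visit; no dropout; the difference taken as 30% TAU v 10% intervention; accurate recall; days independent given each man's own long-run probability p; p follows a Beta distribution with precision M, shown as a range.

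**1. The plan's own figures.** Power = Φ[(|p1 − p2| − 1.96·SE0)/SE1], with SE0 pooled and SE1 unpooled.
- Odds ratio 3 upward from 30% gives 56%, and power at 40 v 80 is 78.8%. This fits the stated odds ratio if 80% power was intended.
- For 30% v 10% (odds ratio 3.86), the pooled rate is (12 + 8)/120 = 0.167, SE0 = √(0.167 × 0.833 × (1/40 + 1/80)) = 0.0722 and SE1 = √(0.21/40 + 0.09/80) = 0.0798. Power = Φ[(0.20 − 0.1415)/0.0798] = 77%. This is the benchmark below.
- The stated interval of 2% to 28% is not reproduced: Newcombe's method for 30% v 10% at 40 v 80 gives 5.3% to 36.2%. That is a separate matter.

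**2. The rule on seven doses.** One missed is 6/7 = 85.7%, not suboptimal. Two missed is 5/7 = 71.4%, suboptimal. So <80% is identical to missed 2 or more. This step needs only daily dosing.

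**3. Noise for one man.** P(flagged | p) = 1 − p⁷ − 7p⁶(1 − p).

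| Long-run adherence p | Weeks flagged suboptimal |
|---|---|
| 0.75 | 55.5% (so 44.5% pass) |
| 0.80 | 42% |
| 0.85 | 28% |
| 0.90 | 15% |

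**4. Noise over the trial.** For each M, the Beta mean is set so that 30% (TAU) or 10% (intervention) of men have p < 0.80, and step 3 is averaged over that distribution. Example, TAU at M = 4: sensitivity 72.6% and specificity 89.5%, so misclassified = 0.30 × 0.274 + 0.70 × 0.105 = 15.6%. Overall = (TAU + 2 × intervention)/3.

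| M | Misclassified TAU / intervention / overall | Difference seen, seven-day rule | Difference seen, four-week rule | Power, seven-day rule |
|---|---|---|---|---|
| 4 | 16% / 7% / 10% | 18 points | 20 | 68% |
| 8 | 21% / 11% / 14% | 17 | 20 | 60% |
| 15 | 26% / 15% / 19% | 15 | 19 | 47% |
| 30 | 31% / 21% / 24% | 13 | 18 | 33% |

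The four-week column models that item as missed 6 or more of 28 (22/28 = 78.6%). In the TAU arm the two 80% labels disagree for 13%, 17%, 21% and 25% of men at the same visit by chance alone.

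**5. Other spreads.**
- Strongly skewed adherence (M = 1-2): 5-7% misclassified overall, 18.7-19.2 points, power 73-75%.
- Logit-normal spread, SD 0.75-1.5: 11-19% overall, 14.6-17.8 points.
- Strong week-to-week clustering at M = 10: 27% TAU, 15% intervention, 13.6 points, against 22%, 12% and 16.5 points without it.
- Realised 28-day adherence as the target, M = 5-20: 14-23% TAU, 7-15% intervention.

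**6. The count from the same item.** Simulated power at M = 4, 8, 15 and 30 is about 86%, 78%, 62% and 41% for a rank test on 0-7. For an overdispersed grouped-binomial test it is 80%, 76%, 64% and 42%, against 68%, 61%, 50% and 33% for the binary in the same run. Runs differ by a few points.

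**The case against.** The strongest reply is that the rule is not false. Each item is defined over its own recall window, and a man who missed 2 of 7 doses did take less than 80% that week. Two windows can legitimately disagree. The four-week rule is also imperfect against long-run adherence: it misclassifies 9-23% of TAU men over the same range. This stands. The complaint is inefficiency and a label that suggests overall adherence, not an error of definition.

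A reader might infer that 20-30% of the men are put on the wrong side of 80%. The documents do not support that. It fits only an arm with 30% suboptimal, at middling to high precision. Two-thirds of the men are in the intervention arm, where the assumed rate is 10%, and the whole-trial figure is 10-24%, or 5-7% under strong skew.

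A reader might also infer that a planned 20-point effect is lost. The power paragraph states a detectable difference, not a planned one, leaves its direction open and does not tie it to the seven-day item. The attenuation therefore cannot be charged to that figure.

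Finally, the harm is limited. The four-week item keeps about 18-20 points, DBS levels are collected, the planned model uses both follow-ups rather than one visit, and the study describes itself as a feasibility study. The gain from the count also assumes that the intervention shifts the whole adherence distribution. Under strong skew the gain is smaller, and the binomial test has about the same power as the binary at precision 1. All of this lowers the severity. It does not supply a reason to discard the count.

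**Conclusion.** The point holds as a cheap improvement of minor severity. That the seven-day rule equals missed 2 or more of 7 is arithmetic, given daily dosing. That it is a noisy indicator of taking less than 80% of all doses follows from the binomial with independent days.

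The size depends on a spread of adherence that the documents do not give, so it should be quoted only as a range. With 30% v 10% truly below 80% and precision 4 to 30, a 20-point difference appears as about 18 to 13 points, and one-visit power drops from 77% to about 68-33%. The lower end requires few men with near-perfect adherence; with strongly skewed adherence the loss is only about 1 point. The difference shrank under every spread examined. The count had more power than the binary at every precision of 2 or more.

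**What to change.** - **PrEP adherence paragraph:** restrict the under-80% definition to the four-week percentage.
- **Statistical analyses:** analyse the seven-day item as doses missed out of 7 in the random-intercept model already planned, with an overdispersed grouped-binomial or ordinal outcome. Report the difference in mean missed doses per week.
- **If a binary seven-day version is kept for description:** label it *missed 2 or more of 7 doses*, not as 80% adherence.
- **Statistical power:** state which adherence measure the detectable difference of about 20% refers to.

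The cost is wording only. The item is already collected as a count, so no extra data, visits or participants are needed. The one downside is that the seven-day effect no longer shares a yes/no scale with the four-week measure.
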